# b. Data Analysis:

- Primary and secondary outcomes of interest will be studied as outlined above. Data will be presented as mean ± standard deviation, median [interquartile range; range], and count (percentage), as appropriate. Data will be graphed, QQ plots performed and Shapiro-Wilk test utilized to assess for normality. Statistical tests for primary and secondary outcome will be compared using independent samples t-test and Mann-Whitney U test, as appropriate. Categorical variables were investigated using Pearson's Chi-Square. Statistical significance will be assigned at 0.05. All data will be analyzed using the R statistical software.

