after transition to PO opioids. The modality of IV opioid administration will revert to the assigned treatment arm.

- Other aspects of each patient's routine clinical care will continue as per the attending physician under whom the patient is admitted regardless of treatment arm status (PDA vs PCA).
- At the end of their hospital stay, we will document the following outcomes:
  - 1. Primary outcome: Length of stay (days)
  - 2. Secondary outcomes:
  - a. Number of hours the patient is NPO before diet is initiated
  - b. Mean pain scores on NRS over the first 24 hours, second 24 hours and course of their hospital stay
  - c. Total opioid dose for pain control during hospitalization (average MME during hospital stay)
  - d. Time to transition to PO opioids
  - e. Opioid-related adverse events/side effects: respiratory decompensation, sleep-disordered breathing, hypotension, nausea, vomiting, constipation, drowsiness, confusion, delirium or other mental status changes, myoclonus, headache, urinary retention, physician suspected opioid abuse or any form of allergic reaction.
  - f. Use of naloxone and antiemetics
  - g. Number of rescue doses required daily and in total through the hospital stay
  - h. ICU transfer
  - i. 30-day readmission rates
  - j. All-cause inpatient mortality and opioid-related inpatient mortality
  - k. 30-day mortality
  - I. Daily MME on discharge
- We expect to enroll patients over a 36-month period from the start date of the study. Based on this, we expect patient enrollment to end by 4/30/2024. We will plan to perform data analysis at two points: 1. Interim data analysis at a predetermined point in the study (mid-point of study), and 2. At the end of the study once patient enrollment has been completed.

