#### B. Statistical Considerations

# a. Sample Size Justification:

- Data from a retrospective study of acute pancreatitis patients receiving either patient-controlled analgesia (PCA, n=116) or conventional IV push (IVP, n=647) showed that mean length of stay was higher in the PCA group (9.9 ± 7.14 days) compared to the IVP group (6.4 ± 9.86 days). The effect size calculated using this data yielded a Cohen's d=0.42. Therefore, assuming a 5% error probability for two groups, the estimated sample size to achieve 80% statistical power was determined to be 87 patients per group. At the midpoint of the study when half of target sample size is reached, preliminary post-hoc analysis will be performed to determine effect size and statistical power.

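### The primary test for length of stay is not fixed in advance: the trial is sized on mean days, but a normality check on the trial data points to a rank test, which has a different target

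*Combined protocol and SAP*

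**What the plan says.** Section B3.A gives the primary outcome as length of stay in days and names no summary measure (mean, median, ratio or other).

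Section B3.B.a (Sample Size Justification) is written in means. In a retrospective comparison, "mean length of stay was higher in the PCA group": 9.9 (SD 7.14) days in 116 PCA patients against 6.4 (SD 9.86) days in 647 IV-push patients. It continues: "The effect size calculated using this data yielded a Cohen's d=0.42". With a 5% error probability and 80% power this leads to 87 patients per group.

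Section B3.B.b (Data Analysis) says that the data will be graphed, with "QQ plots performed and Shapiro-Wilk test utilized to assess for normality". The choice of test follows: "Statistical tests for primary and secondary outcome will be compared using independent samples t-test and Mann-Whitney U test, as appropriate". Results may be shown as mean with SD or as median with interquartile range. No threshold or decision rule links the normality check to a test, and nothing separates the primary outcome from the secondary ones.

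**The concern.** The two candidate tests answer different questions. The t-test compares mean stay. Mann-Whitney asks whether a stay in one arm tends to exceed a stay in the other. With symmetric data of equal spread the two largely coincide. With skewed data of unequal spread they can disagree on the same trial.

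The trial is sized for the first question. The quoted SDs are close to or above the means, and stay cannot be negative, so the data will be strongly right-skewed and a normality check will point to the second. A significant primary result could then be reported as a difference in length of stay when mean stay, the quantity that was powered, does not differ. The stated 80% power would also describe a test that was not run. If the normality check is not a firm rule, the choice rests on judgement made with the outcome data in view, possibly as early as the planned mid-point analysis.

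**Working it through.** **Inputs from section B3.B.a.** Means 9.9 and 6.4 days (difference 3.5), SDs 7.14 and 9.86, d = 0.42, alpha 0.05, power 80%, 87 per arm. Sidedness is not stated; two-sided is assumed.

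**1. Is the trial sized on means?** For a two-sided comparison of means, n per arm = 2(1.960 + 0.842)² / d² = 2 × 7.849 / 0.1764 = 89.0. The plan states 87, which is within 2 patients. One-sided alpha gives 71, which does not fit. So the stated figure is a two-sided calculation for a difference in means. Power at 87 per arm and d = 0.42 is Φ(0.42 × √(87/2) − 1.960) = Φ(0.81) = 79%.

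**2. Where does the normality check lead?** I simulated 4,000 trials per setting, with 87 per arm and lognormal or gamma stays matched to the stated mean and SD. Shapiro-Wilk at 0.05 in either arm selected Mann-Whitney; otherwise the t-test was used. Shapiro-Wilk rejected in essentially 100% of trials in every setting, including a milder one (mean 6.4, SDs 4 and 5).

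**3. Both arms from one distribution.** The gated procedure was significant in 4.7–5.5% of trials, so there is no inflation under this null.

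**4. Equal means, unequal spreads.** The documents give no common mean, so 6.4, 8.15 and 9.9 days were assumed.

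| Common mean | SDs | Shape | Mann-Whitney p < 0.05 | Welch p < 0.05 |
|---|---|---|---|---|
| 6.4 | 7.14 vs 9.86 | lognormal | 25.4% | 5.0% |
| 8.15 | 7.14 vs 9.86 | lognormal | 23.4% | 4.9% |
| 9.9 | 7.14 vs 9.86 | lognormal | 21.5% | 4.9% |
| 6.4 | 7.14 vs 9.86 | gamma | 43.2% | 5.4% |
| 8.15 | 7.14 vs 9.86 | gamma | 30.0% | 5.1% |
| 9.9 | 7.14 vs 9.86 | gamma | 22.0% | 5.1% |
| 6.4 | 4 vs 5 | lognormal | 11.5% | 5.1% |
| 6.4 | 4 vs 5 | gamma | 10.5% | 5.2% |

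Repeat runs with other random seeds put the first six Mann-Whitney rows at about 20–45%. At a common mean of 8 with SDs of 8 vs 9 or 7.5 vs 8.5, Mann-Whitney was significant in about 7–8%. Rounding stays to whole days left 23% (lognormal, mean 6.4).

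**5. Why the tests part.** A lognormal median is mean / √(1 + (SD/mean)²). At mean 6.4:
- SD 7.14: 6.4 / √2.245 = 4.3 days
- SD 9.86: 6.4 / √3.374 = 3.5 days

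Equal means therefore go with different medians, and the chance that a stay from the first arm exceeds one from the second is about 0.56. Mann-Whitney responds to that.

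**6. At the planning means (9.9 vs 6.4).** Mann-Whitney was significant in over 99% of trials and Welch in about 74–78%. The normal approximation agrees for Welch: the standard error is √((7.14² + 9.86²)/87) = √(148.2/87) = 1.305, and Φ(3.5/1.305 − 1.960) = Φ(0.72) = 76%. This is below 80% because the quoted SDs in equal arms give d = 3.5/√(148.2/2) = 0.41 rather than 0.42, and 87 is slightly low even for 0.42.

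**The case against.** **The 20–45% is not a false-positive rate.** A reader might infer that the plan inflates type I error to that level. It does not: with one common distribution the procedure holds about 5%. In the equal-mean scenario the arms do differ (medians 4.3 vs 3.5 days), and a significant rank test detects something real, though not a difference in means. This stands, and it limits the point to a mismatch of target.

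**The SD gap is borrowed.** It comes from a non-randomised comparison of 116 and 647 patients whose means also differed. Nothing in the documents says that a randomised trial with no mean effect would show so large a gap. This stands too; with smaller gaps the figure is about 7–11%.

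**No sentence ties Shapiro-Wilk to Mann-Whitney.** A reader might infer that Mann-Whitney is certain to decide the trial. That is the natural reading of a normality check followed by an open choice, but it is not written. It could also be said that a check which always rejects leaves no data-dependent choice. In that case the mismatch of target remains; if the check is not a rule, the choice is open. The remedy is the same either way.

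**The mean is not a declared estimand.** Cohen's d can be a planning device, and a rank analysis of skewed stay is defensible. This stands: the plan may choose either target but has chosen neither.

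**Power.** A reader might infer that Mann-Whitney would leave the trial underpowered. At the planning values it has more power than Welch, for a different question. The ordering depends on shape: for gamma stays with each SD equal to its mean, Mann-Whitney has about 69% and Welch about 81%.

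**Conclusion.** The point holds in limited form. The primary test and summary measure are not fixed, the trial is sized on mean days, and the natural reading of the analysis section leads to a test that does not target mean stay.

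How much this matters depends on how far the spreads differ between arms. With equal means, a significant Mann-Whitney occurs in about 20–45% of trials at the cited SDs and about 7–11% at smaller gaps, against about 5% for Welch throughout. These figures assume lognormal or gamma stays, 87 per arm, common means between 6.4 and 9.9 days, and two-sided 0.05. The unfixed test is a fault whatever the spreads turn out to be.

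**What to change.** For the primary outcome, remove the normality check as a selector and state one test and one summary measure before any outcome data are seen, including at the mid-point analysis.

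- **To match the sample size:** difference in mean stay (PCA minus PDA) by Welch's t-test, or regression on arm with robust standard errors, with a 95% CI. Report Mann-Whitney with the Hodges-Lehmann shift as supportive.
- **If a rank-based target is preferred:** name it as primary in advance and restate the power for it under stated distributional assumptions.

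The text change is about one sentence, but it has two costs. The mean is sensitive to a few very long stays, which the supportive rank analysis helps to show. Welch's power at the quoted means and SDs is about 74–78%, so the 80% statement must be corrected or the sample enlarged. On the normal approximation, 80% needs 7.849 × 148.2 / 3.5² = 95 per arm, or 190 in total against 174.

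### As many as 30 secondary comparisons fall under one unadjusted 0.05 rule; with no true effects, the chance of at least one false significant result is roughly 35% to 79%

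*Combined protocol and SAP*

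**What the plan says.** The protocol names one primary outcome, length of stay, and 12 lettered secondary items (a to l) in the outcome list of section B3.A. Several items contain more than one quantity. Item b alone asks for "Mean pain scores on NRS over the first 24 hours, second 24 hours and course of their hospital stay". Item e opens with "Opioid-related adverse events/side effects: respiratory decompensation, sleep-disordered breathing, hypotension, nausea, vomiting" and continues to 14 named events.

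The Data Analysis section (B3.B.b) then says: "Statistical tests for primary and secondary outcome will be compared using independent samples t-test and Mann-Whitney U test, as appropriate". For binary outcomes it says: "Categorical variables were investigated using Pearson's Chi-Square". The threshold is given once, for everything: "Statistical significance will be assigned at 0.05".

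The document contains no multiplicity adjustment, no testing order and no key secondary outcome. It does not describe the secondary outcomes as exploratory or descriptive. It also does not say whether each adverse event is tested on its own, or whether the chi-square test carries a continuity correction.

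**The concern.** Under the rule as written, any secondary outcome with p<0.05 may be reported as statistically significant, in either direction. With a list this long, at least one such result can readily arise by chance. Fourteen of the possible comparisons are opioid adverse events, so a chance result could be read as harm from patient-controlled analgesia or as a safety advantage. Section B4 hopes for better pain control and an earlier move to oral analgesics, both of which are measured among the secondary outcomes. The error rate attached to claims of that kind is therefore of practical interest.

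The issue arises at the final analysis alone and does not depend on the planned interim look.

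**Working it through.** **The plan's own figures.** The document states no family-wise error rate. The figures used here are the 0.05 level (B3.B.b, taken as two-sided because sidedness is not stated) and 87 patients per arm (B3.B.a and B3.C). The 87 is reproduced closely: with d = 0.42 and 80% power, n = 2(1.960 + 0.842)²/0.42² ≈ 89 per arm (90 with the t distribution), and power at 87 per arm is about 79%.

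**Counting the comparisons (B3.A, items a to l).**

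| Item | Content | Comparisons |
|---|---|---|
| a | Hours NPO | 1 |
| b | Mean NRS, three windows | 3 |
| c | Opioid dose in hospital | 1 |
| d | Time to oral opioids | 1 |
| e | Adverse events | 14 |
| f | Naloxone, antiemetics | 2 |
| g | Rescue doses, daily and total | 2 |
| h | ICU transfer | 1 |
| i | 30-day readmission | 1 |
| j | Inpatient deaths, all-cause and opioid-related | 2 |
| k | 30-day mortality | 1 |
| l | Daily MME on discharge | 1 |
| | **Total** | **30** |

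Nine of these are continuous or counts (a, b, c, d, g, l) and 21 are binary (e, f, h, i, j, k). If the adverse events form one comparison, the total is 30 − 14 + 1 = 17. With one test per lettered item it is 12.

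**Independent tests, no true effects, each with true size 5%.** P(at least one p<0.05) = 1 − 0.95^k, and the expected number of false positives is 0.05k.

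- k = 30: 78.5%, with 1.5 expected
- k = 17: 58.2%, with 0.85 expected
- k = 12: 46.0%, with 0.60 expected

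**Correlated tests.** The document gives no correlations, so these are assumptions. Test statistics were simulated as Z = √ρ·F + √(1−ρ)·E, with F common to all tests, rejecting when |Z| > 1.96 (200,000 sets).

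| Tests | ρ = 0 | ρ = 0.3 | ρ = 0.5 | ρ = 0.6 |
|---|---|---|---|---|
| 30 | 79% | 66% | 51% | 42% |
| 17 | 58% | 49% | 39% | 33% |
| 12 | 46% | 40% | 32% | 28% |

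**Rare events.** At 87 per arm the chi-square test cannot use its full 5% on rare outcomes. For a 3 versus 0 split, χ² = (3/87)² / [(3/174)(171/174)(2/87)] ≈ 3.05, below the critical value of 3.84. The exact null size is about 1.0% at a 1% event rate (0.02% with continuity correction) and about 0.1% at a 0.5% rate. At a 10% rate it is 5.0% without correction and 2.4% with it.

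**Putting these together.** Event rates from 0.1% to 40% were assumed for the 21 binary outcomes, with 5% size for the other nine.

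| Scenario, 30 outcomes | Uncorrected | Continuity-corrected |
|---|---|---|
| Independent | 68% | 53% |
| Independent, rates halved | 62% | 48% |
| Correlation 0.3 continuous, 0.1 binary | 65% | 49% |
| Correlation 0.5 continuous, 0.3 binary | 61% | 43% |
| Correlation 0.7 continuous, 0.3 binary | 55% | 36% |

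For all 30 outcomes, then, the realistic cases run from about 36% to 68%, and 78.5% is close to an upper figure. Fewer tests combined with strong correlation can fall a little below 35%, as the 12-test row of the correlation table shows.

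**The case against.** The strongest reply is that the trial has one primary outcome, tested once at the final analysis at 0.05, and that the number of secondary outcomes does nothing to that error rate. Reading unadjusted secondary outcomes as supportive is a common and defensible convention. This stands as far as the primary outcome goes. It does not cover the secondary outcomes, because the plan never calls them supportive or exploratory; it gives them the same significance rule as the primary.

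A second reply is that 30 is a reader's count. The plan has 12 lettered items, item e may be meant as a single grouped comparison, several outcomes overlap or are nested (the pain windows, opioid and rescue doses, the mortality items), and deaths can hardly reach significance at this size. This also stands, and it is why the result is given as a range.

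Two stronger readings are tempting, and the document supports neither:

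- **A reader might infer that a false significant result is more likely than not.** That holds for 30 full-size tests with correlation up to about 0.5. It fails with 12 tests, with 17 tests at correlation 0.3, and with a continuity correction once outcomes are correlated.
- **A reader might infer that the trial will miss on length of stay and rest its conclusion on whichever secondary outcome reaches 0.05.** Nothing in the text says so. At the planned effect of d = 0.42 the primary comparison has about 79% power.

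**Conclusion.** The point holds in a limited form. The stated rule permits significance claims on 12 to 30 secondary comparisons without ranking, adjustment or an exploratory label. With no true effects, the chance of at least one false claim among them is roughly 35% to 79%. Where it falls depends on how many are tested, how strongly they are correlated, how common the events are and whether a continuity correction is used. Event rates and correlations are assumptions, since the document gives none. Even the low end is about seven times the nominal 5% (0.35/0.05 = 7), so the need for a change does not turn on whether the chance exceeds one half. The primary outcome's 0.05 level is untouched.

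This is a cheap improvement rather than a defect in the main comparison. Confidence is moderate, because the number of tests actually intended is not stated.

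**What to change.** In the Data Analysis section (B3.B.b):

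1. Reserve the 0.05 significance statement for length of stay.
2. State that all secondary outcomes are exploratory and will be reported as between-arm estimates with 95% confidence intervals not adjusted for multiplicity, with no claim of significance; adverse events and deaths will be tabulated by arm.

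If confirmatory secondary claims are wanted, name at most three from the existing list in advance, for example time to oral opioids and mean NRS over the first 24 hours. Test them with Holm at an overall 0.05, and only after a significant primary result. Without that condition, the primary and the secondary family could together reach nearly 0.10 (1 − 0.95² = 0.0975 if independent). Patient satisfaction is measured under B3.A and mentioned in B4 but is not among items a to l, so it would first have to be added as a secondary outcome.

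The cost is about two sentences, with no new data and no extra patients; the optional step adds a little more text. The downside is that a lone p<0.05 on an unranked secondary outcome can no longer be claimed as a finding.

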# C. Subject Selection

We will study 174 patients admitted within 24 hours to the hospital with AP between 18 and 65 years of age. Patients will be randomized to receive IV opioids either via PCA (n=87) or PDA (n=87). Exclusion criteria are as follows: known allergy or contraindication to opioids, active illicit drug use, chronic pancreatitis, pancreatic cancer, acute encephalopathy/psychiatric illness that would preclude ability to use PCA, chronic renal insufficiency with a Cr >2, acute renal insufficiency with a Cr >3, and known allergy to acetaminophen or hepatic dysfunction otherwise limiting acteaminophen use.

Inclusion criteria	Exclusion criteria
Diagnosis of AP confirmed by revised Atlanta criteria	Active illicit drug use
	Discharged from the ED
Admitted to the medical floor within 48 hours of ED arrival	Direct admission to ICU from ED
	Known allergy to opioid medications
Age 18-65	Age <18 or >65
	Known chronic pain syndrome or concurrent medical condition with chronic pain
	Active
	encephalopathy/confusion/delirium/psychiatric

Study Description – Part B CCI Form: 9-2015 PI Revision Date: 3/2/2021

illness or any other condition that limits capacity
Known chronic opioid use
Renal insufficiency (baseline Creatinine of >2 and/or AKI with Cr>3 on admission)
Known allergy to acetaminophen or hepatic dysfunction otherwise limiting acetaminophen use

Subjects will be enrolled without regard to race, gender, or vulnerable category status.

#### **B4. POSSIBLE BENEFITS**

Patients in this study will obtain no direct benefits from participation in the study. We hypothesize that based on prior studies in postsurgical patients, patients in the PCA arm may potentially have better control of their AP-related pain as compared to conventional physician directed analgesia. This may potentially result in higher patient satisfaction, early transition to oral analgesics, and shorter hospital stays. This information will be helpful in better management of the patients' pain with a PCA protocol in the future.

# B5. POSSIBLE RISKS AND ANALYSIS OF RISK/BENEFIT RATIO

Patients enrolled in either arm of opioid administration are at risk of developing opioid-related adverse events. These range from minor gastrointestinal side effects such as nausea and vomiting to life-threatening cardiorespiratory decompensation and even death. However, pain control with opioids is the standard of care in treating pain associated with AP, and hence, our study does not impose any additional risk of opioid-related adverse events than what would be expected normally in these patients. However, we do acknowledge the risks associated with use of a PCA pump. Since opioid administration is controlled by the patient, there remains risk of delivering a higher opioid dose in a short duration of time, which may predispose the patient to potential acute opioid intoxication. However, our protocol has been designed to deliver lower individual doses of opioid with each dose when compared to PDA. Additionally, the patients will be closely monitored by vital sign measurement by the nursing staff as part of the usual care of AP patients, with availability of opioid reversal agents if needed

## **B6. RECRUITMENT AND CONSENT PROCEDURES**

## Recruitment

Patients will be identified as they are admitted to the hospital for management of AP. Our research staff will check with the admitting hospitalists/physicians on a daily basis for patients admitted with AP who may be eligible for enrollment in the study. Once we have identified a patient who meets the study criteria, our research staff will approach the patient and obtain informed consent.

# Consent

After identifying a potentially eligible inpatient, a study Investigator will fully explain the purpose of this study to the patient. After fully answering the patient's questions and if the patient's consents to entering the study, a signed consent will be obtained. A study investigator will be responsible for obtaining written informed consent from each patient. The patient will be given a copy of the informed consent form, a copy will be placed in the patient's medical record and the original will be kept in the research files.

